6.1.1 Allogeneic Stem Cell Transplant

Patients with intermediate and high-risk disease by cytogenetics and/or molecular studies should be considered for allogeneic transplant while in first remission. The transplantation, including donor selection, will not be guided by this protocol but will be at the discretion of the treating physician.

6.1.2 Positive for FLT-3

Patients found to be positive for FLT-3 may have midostaurin added to induction and consolidation per approved indications

6.2 Imaging exams

Upon enrollment, subjects will be scheduled for the echocardiogram, cardiac MRI exam and clinic visit for labwork. For the Ultrasound portion of the study, the subject will go to the Clinical Ultrasound lab. After arrival at the ultrasound lab, the subject will be positioned on a scanning bed with ECG leads attached. Then an ultrasound transducer will be placed on the subject's chest and pictures will be taken of the heart using three-dimensional imaging and spectral Doppler techniques. The total time of the ultrasound testing will be 45 minutes. The MRI exam will be performed in the CMR suite where they will be placed supine on the CMR table and ECG leads and respiratory gating bellows applied. CMR scans will be performed on a 1.5 Tesla GE CVi scanner with a phased array surface coil applied around the chest to optimize signal to noise. All images will be acquired using a fast gradient echo technique, with the repetition time (TR) and echo time (TE) based on the R-R interval of the subject. Multi-slice coronal, gradient echo sequences will be used to obtain scout images of the chest and locate the left ventricle. After locating the LV a series of steady state free precession, short axis views will be

**CYTARABINE PLUS CONTINUOUS INFUSION DAUNORUBICIN, WITH CARDIAC
MRI MONITORING, INDUCTION THERAPY FOR ADULTS WITH ACUTE MYELOID
LEUKEMIA; A FEASIBILITY STUDY**

Wake Forest Baptist Comprehensive Cancer Center (WFBCCC) CCCWFU 22616

acquired perpendicular to the left ventricle covering from the base to the apex; imaging parameters were 32cm field of view, 35° flip angle, 8mm slice thickness, 2mm inter-slice space, and a 256X128 matrix. These scans will incorporate a temporal resolution of 40msec in order to identify end-systole for the determinations of LV volumes, EF, and mass. This protocol will be identical to that implemented in CCWFU 98998 and the Multi-Ethnic Study of Atherosclerosis.¹³

6.3 Analysis of MRI images

For LV mass, volume, and EF determinations, calculations will be performed according to widely published and currently accepted techniques that are in current use at or institution in single and multi-center trials. The epi- and endocardial border of each slice from the multi automated drawing program, and assessments will be calculated by summation (Simpson's rule). Basal slices will be reviewed in cine format to resolve structures for inclusion (the aortic outflow tract) or exclusion (left atrium and mitral leaflets) from the mass, volume, and EF measurements.

6.4 General Concomitant Medication and Supportive Care Guidelines

Patients should receive *full supportive care*, including transfusions of blood and blood products, erythropoietin, antibiotics, antiemetics, etc., as clinically indicated. Anti-inflammatory or narcotic analgesics may be offered as needed. Medications considered necessary for the patient's well-being may be given at the discretion of the investigator, i.e., chronic treatments for concomitant medical conditions, as well as agents required for life-threatening medical problems, etc. The reason(s) for treatment, dosage, and dates of treatment should be recorded on the flow sheets.

6.5 Duration of Therapy

Treatment under this protocol may continue until one of the following criteria applies:

- Allogeneic stem cell transplant,
- Disease progression,
- Intercurrent illness that prevents further administration of treatment,
- Unacceptable adverse event(s),
- Patient decides to withdraw from the study, or
- General or specific changes in the patient's condition render the patient unacceptable for further treatment in the judgment of the investigator.

6.6 Duration of Follow Up

Patients will have an MRI without contrast and full/limited ECHO at 3 months or relapse, whichever occurs first. Patients still on protocol at 6 months post-treatment will have an MRI without contrast only.

Patients will be followed for a minimum of 30 days after the last study drug is administered or until death, whichever occurs first, for adverse events monitoring. Patients removed from the study for unacceptable adverse events will be followed until resolution or stabilization of the adverse event.

CYTARABINE PLUS CONTINUOUS INFUSION DAUNORUBICIN, WITH CARDIAC
MRI MONITORING, INDUCTION THERAPY FOR ADULTS WITH ACUTE MYELOID
LEUKEMIA; A FEASIBILITY STUDY

Wake Forest Baptist Comprehensive Cancer Center (WFBCCC) CCCWFU 22616

Patients will be followed by phone call every 3 months for monitoring survival endpoints.

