2.0 Objectives

2.1 Primary Objectives

- 2.1.1 To assess the safety (at 3 months) and feasibility of administering daunorubicin as continuous infusion under the proposed treatment regimen.

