5.0 Study Outcomes

5.1 Primary Outcomes

- 5.1.1 Cardiac toxicity(see 2.2.3), as measured by MRI (ejection fraction [EF], left ventricular end diastolic volume [LVEDV], left ventricular end systolic volume [LVESV], T1/T2 mapping and myocardial strain) measures and ECHO (EF, myocardial strain, LVEDV, LVESV, ESV, mitral inflow E, A, E' and A') measures. Cardiac toxicity is defined as reduction in LVEF of $\geq 10\%$ compared to baseline LVEF and $EF \leq 50\%$ on the follow-up scan. This assessment will be performed using both an ECHO and MRI measure. In addition, the primary outcome will be assessed at the 3 month follow-up (or relapse) visit.
- 5.1.2 Other unexpected toxicities (exclude hematologic and infectious) \geq grade 3, as measured by CTCAE v 4.0
- 5.1.3 Feasibility, as measured by ability to administer continuous infusion daunorubicin and complete required study assessments with limited deviation from the proposed regimen (as defined in section 8.2)

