8.2 Definitions

- Study Regime: Completion of the critical study regime tasks will be tracked by research staff and recorded as “Yes” or “No” in Appendix E, The Cardiac Function form. The tasks that should be recorded in this manner are the following:
 - The daunorubicin infusion (Induction):
 - if this is not completed in 72 hours +/- 1, record as “No”,
 - If the infusion is completed within these parameters record “yes”.
 - If “No”, record the total infusion amount and time taken to administer.

**CYTARABINE PLUS CONTINUOUS INFUSION DAUNORUBICIN, WITH CARDIAC
MRI MONITORING, INDUCTION THERAPY FOR ADULTS WITH ACUTE MYELOID
LEUKEMIA; A FEASIBILITY STUDY**

Wake Forest Baptist Comprehensive Cancer Center (WFBCCC) CCCWFU 22616

- ECHO (at pre-induction visit, *post-treatment (pre-discharge), 3 month follow-up or relapse):
 - Record “Yes” or “No” if the patient completes or does not complete the ECHO at each visit.
 - *indicates an additional assessment for those individuals requiring a second cycle of Induction therapy
- MRI (at pre-induction visit, 3 month follow-up or relapse, at 6 month follow-up or relapse):
 - Record “Yes” or “No” if the patient completes or does not complete the MRI at each visit.
- Evaluable for toxicity: All patients will be evaluable for toxicity from the time of their first treatment with daunorubicin.
- Persistent leukemia: Patients not achieving a remission after 2 induction attempts; these patients will be removed from the study.
- Disease-free survival: calculated for patients who achieve CR and measured from the date of CR until relapse from CR or death. Observation is censored at the date of last follow-up for patients last known to be alive without report of relapse.
- Time to death: calculated from date of study registration to date of death due to any cause. Patients last known to be alive are censored at date of last contact.

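### Scans taken after an off-protocol allogeneic transplant can enter the primary 3-month cardiotoxicity result unmarked

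*Combined protocol and SAP*

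**What the plan says.** The primary objective (Section 2.1) concerns 3-month safety and "feasibility of administering daunorubicin as continuous infusion under the proposed treatment regimen". For the cardiac endpoint, Section 5.1 states that "the primary outcome will be assessed at the 3 month follow-up (or relapse) visit". Section 6.6 sets the schedule: "Patients will have an MRI without contrast and full/limited ECHO at 3 months or relapse, whichever occurs first". Section 8.2 repeats it for the MRI, "MRI (at pre-induction visit, 3 month follow-up or relapse, at 6 month follow-up or relapse", and the column headings of Appendix E match. Relapse is the only alternative trigger in all four places.

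Section 6.1.1 says that patients at intermediate or high cytogenetic or molecular risk "should be considered for allogeneic transplant while in first remission", and adds: "The transplantation, including donor selection, will not be guided by this protocol". Section 6.5 lists "Allogeneic stem cell transplant" among the events that end protocol treatment. Section 6.1 also names transplant as a reason for not completing consolidation.

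No section ends cardiac follow-up at transplant. The condition of still being on protocol is attached in Section 6.6 to the 6-month MRI only. Section 8.2 makes patients evaluable for toxicity from their first daunorubicin and gives no end point.

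Section 13.1 plans paired t-tests of change from baseline and the proportion with a cardiotoxic event at 3 months, with a 95% confidence interval. Section 13.2 repeats the toxicity analyses at 6 months. Neither mentions transplant. Appendix D records whether a transplant was given and its date; the Appendix E worksheet has no such field.

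**The concern.** The study has one arm and reads cardiac safety from each patient's change since baseline. Whatever happens between the two scans is therefore part of the estimate. High-dose cytarabine consolidation also comes between them, but it belongs to the regimen under study. Transplant treatment does not: the protocol disclaims control of it and stops protocol treatment when it occurs.

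A patient transplanted before the 3-month visit still appears to be due a scan, and that scan counts like any other. If transplant treatment changed ejection fraction, volumes, strain or T1/T2 values, the change would be reported as a finding about the regimen. Exposure would not be random, because Section 6.1.1 ties consideration for transplant to disease risk. As planned, a reader of the results could not tell how many primary scans were affected.

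**Working it through.** **1. The plan's own figures (Section 13.3).** Inputs: 32 evaluable, 20% drop-out, 80% power, two-sided α = 0.05, paired t-test, exact interval.
- Enrolment: 32 / (1 − 0.20) = 40.
- Detectable difference d, solving P(|T| > t(0.975, n − 1)) = 0.80 for a noncentral t with noncentrality d√n: 0.5113 SD at n = 32 and 0.4543 SD at n = 40, against 0.511 and 0.45 stated.
- Clopper-Pearson interval at 16/32: 0.3189 to 0.6811, half-width 0.1811, against 0.181 stated.

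All reproduce. The point is about what is measured, not about the sample size.

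**2. Event rate if post-transplant scans are pooled.** Let f be the share transplanted before the scan, p0 the event rate without transplant and p1 the rate after it. Pooled rate = (1 − f)p0 + f·p1. The documents give none of these. Assume f = 10–40% (about 3 to 13 of 32), p0 = 10% and p1 = 10–25%.
- p1 = 10% (no effect): 10% for every f.
- f = 10%, p1 = 25%: 0.9 × 10% + 0.1 × 25% = 11.5%.
- f = 40%, p1 = 25%: 0.6 × 10% + 0.4 × 25% = 16.0%.

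The shift is 0 to 6 percentage points, or at most 0.06 × 32 = 1.9 events. The stated ±0.181 applies at a 50% rate. Nearer the assumed rate, 3/32 gives 0.0198 to 0.2502, half-width 0.115, and 6 points is inside that too.

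**3. Paired t-test.** If transplant treatment shifts a patient's change by s SD, the mean shifts by f·s. This ignores the small effect of mixing on the SD. With f = 20% and s = 0.5 the shift is 0.10 SD, and the n = 32 test rejects 8.5% of the time with no effect of the regimen, instead of 5%. A shift of 0.20 SD (for example f = 40%, s = 0.5) gives 19.5%. With s = 0 it stays at 5%.

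**4. Cost of leaving those scans out.**

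| Scans left out of 32 | Detectable difference (SD) | Half-width near a 50% rate |
|---|---|---|
| 0 | 0.511 | 0.181 |
| 3 | 0.539 | 0.190 |
| 6 | 0.572 | 0.201 |
| 10 | 0.626 | 0.218 |
| 13 | 0.680 | 0.233 |

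**5. How much time there is for a transplant before the scan.** Section 6.6 counts the 6-month MRI from the end of treatment but gives no origin for the 3-month scan. Suppose it is counted from induction, with 3 months taken as about day 91. Response is evaluated by day 42, which leaves 91 − 42 = 49 days. But Section 6.1 allows remission to be documented later on a repeat marrow. It also has consolidation start within 14 days of recovery, in cycles of at least 28 days: 42 + 14 + 28 = day 84, which leaves 7 days. Earlier remission, or transplant without consolidation, widens the window again. The documents therefore fix no minimum.

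**The case against.** The strongest reply is that only a missing rule has been shown, not a biased result. No section describes transplant treatment or any cardiac effect of it, and none gives a transplant rate or date. Section 13.1 calls the study a pilot with descriptive analyses, and no threshold or go/no-go decision hangs on the event rate. On the assumed values the shift is smaller than the sampling error. The objective is safety under the regimen, and consideration for transplant sits inside the treatment plan, so including every patient whatever follows is a legitimate choice. Other exposures (high-dose cytarabine, permitted midostaurin, transfusion as supportive care) also precede the scan, so handling transplant would not isolate daunorubicin.

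Most of this stands. It rules out claiming a known bias and supports keeping the all-patients analysis as primary. It does not answer the narrower point. A choice to include all scans should be stated, and the number taken after transplant should be visible. A larger sample would narrow the interval without removing a shift of this kind.

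Transplanted patients might be meant to fall within the 20% drop-out, but no section says so. If they are dropped, the problem becomes selective loss of higher-risk patients.

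**Conclusion.** The gap is real and modest. Nothing in the plan keeps post-transplant scans out of the primary cardiotoxicity rate and paired tests, or marks them there. Its effect may be nil. On the assumptions in the working, the pooled rate is 10–16% against a true 10%.

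A reader might infer more than the documents support:
- **That the primary result is contaminated.** This needs a transplant rate and a cardiac effect that the documents do not give.
- **That about seven weeks are always available for transplant before the scan.** The 49 days is not a floor; the protocol's own steps can reduce it to about 7.
- **That every transplanted patient is scanned after transplant.** This would follow only if the 3-month clock starts at the end of treatment, which is unstated, and even then not for patients who relapse first.
- **That disease-free survival is wrongly defined.** Section 8.2 has it "measured from the date of CR until relapse from CR or death", which is clear and acceptable. Running it through transplant is no error, and censoring at transplant could be informative.
- **That scans at relapse need a further rule for the same reason.** Relapse is already a trigger.

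**What to change.** In Sections 13.1 and 13.2:
- Keep the analysis of all patients as the main one.
- Link the Appendix D transplant date to the scan dates and flag each scan taken after transplant. Section 12.0 puts both forms in REDCap, so no new data are needed.
- Report how many scans are flagged, and give the event rate with its 95% confidence interval and the mean changes with and without them.

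In Sections 5.1 and 6.6, state the date from which the 3-month visit is counted, so that the flag is unambiguous.

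The cost is a few sentences and one derived variable. The analysis without flagged scans has fewer patients: losing 6 of 32 raises the detectable difference from 0.511 to about 0.57 SD. It also leaves out higher-risk patients selectively, so it should be labelled a sensitivity analysis and not read as the effect without transplant. Appendix D holds one date, so the flag cannot identify transplant-related treatment given before that date.

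Making transplant a second trigger for an early scan is an option for the sponsor to weigh. It would keep those patients in the analysis with a scan taken before transplant, but it replaces their 3-month timepoint with an earlier, variable one. The fix does not depend on it.

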2.2 Secondary Objectives

- 2.2.1 To assess the safety (at 6 months) of administering daunorubicin as continuous infusion under the proposed treatment regimen.
- 2.2.2 To assess treatment outcomes (including CR and CRi) in patients with AML under the proposed treatment regimen.
- 2.2.3 To compare the concordance between MRI and ECHO in identifying cardiac toxicity, i.e. a reduction in LVEF of $\geq 10\%$ and $EF \leq 50\%$ compared to baseline LVEF.

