5.2 Secondary Outcomes

- 5.2.1 Cardiac toxicity(see 2.2.2), as measured by MRI (ejection fraction [EF], left ventricular end diastolic volume [LVEDV], left ventricular end systolic volume [LVESV], T1/T2 mapping and myocardial strain) measures and ECHO (EF, myocardial strain, LVEDV, LVESV, ESV, mitral inflow E, A, E' and A') measures. Cardiac toxicity is defined as reduction in LVEF of $\geq 10\%$ compared to baseline LVEF and $EF \leq 50\%$ on the follow-up scan. This assessment will be performed using both an ECHO and MRI measure. In addition, these secondary outcomes will be assessed at the 6 month follow-up (or relapse) visit
- 5.2.2 Treatment outcomes (such as overall response rate) stratified by age (≥ 60 , < 60) and ECOG (0-2, 3): Overall response rate (CR + CRI); Induction death rate; Presence of persistent leukemia; Disease-free survival (for those who achieve remission)
- 5.2.3 Measures of ECHO and MRI derived measures of EF, myocardial strain, LVEDV and LVESV.

CYTARABINE PLUS CONTINUOUS INFUSION DAUNORUBICIN, WITH CARDIAC MRI MONITORING, INDUCTION
THERAPY FOR ADULTS WITH ACUTE MYELOID LEUKEMIA; A FEASIBILITY STUDY
 Wake Forest Baptist Comprehensive Cancer Center (WFBCCC) CCCWFU 22616

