13.0 Statistical Considerations

13.1 Analysis of Primary Objective

Since this is a pilot study, several descriptive analyses will be performed. These will include examining the change in each measure of cardiotoxicity from the initial pre-chemotherapy assessment to each of the available post-chemotherapy imaging assessment (i.e. EF, LVEDV, LVESV, T1/T2 mapping, myocardial strain). These comparisons will be made using paired T-tests. Similar analyses will be performed using the ECHO-derived measures. In addition to examining the continuous changes in measures, we will determine the proportion of patients who exhibit a cardio-toxic event at 3-months defined as have a reduction in LVEF \geq 10% and EF \leq 50% when compared to baseline. This event will be defined for both the ECHO and MRI measures. In addition to point estimates of these rates, 95% confidence intervals will be calculated.

Additional toxicity measures will be tabulated after each visit.

CYTARABINE PLUS CONTINUOUS INFUSION DAUNORUBICIN, WITH CARDIAC
MRI MONITORING, INDUCTION THERAPY FOR ADULTS WITH ACUTE MYELOID
LEUKEMIA; A FEASIBILITY STUDY

Wake Forest Baptist Comprehensive Cancer Center (WFBCCC) CCCWFU 22616

For feasibility assessment, we will determine the proportion of patients with study-related deviations and report these proportions with 95% confidence intervals. In addition, we will determine the proportion of patients who complete the infusion therapy.

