13.2 Analysis of Secondary Objective

Similar toxicity analyses as described above for the primary objective will be examined at the 6-month time point.

We will report frequencies of response status (Overall response rate [CR + CRI]; Induction death rate; Percentage of patients with persistent leukemia; Disease-free survival [for those who achieve remission]) with the number of patients in each category of response. Treatment outcomes will be stratified by age (≥ 60 , < 60), ECOG (0-2, 3), cytogenetic risk groups and prior hematological disease (e.g. MDS, MPN).

Three sets of correlation analyses will be performed; the first will determine the correlation between ECHO and MRI assessments performed pre-chemotherapy; the second will assess correlations between post-chemotherapy ECHO and MRI assessments; and the third will assess correlations between each of the time points. In addition to the correlation analyses, paired t-tests will be performed to compare the actual values of each ECHO/MRI measurement to each other at each time point. Finally, Bland-Altman plots will be generated at baseline, follow-up and using the change in measure for each of the MRI/ECHO derived measures.

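### The 6-month cardiac safety result depends on an undefined on-protocol condition and on available scans only, so it may be biased, plausibly toward understatement

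*Combined protocol and SAP*

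**What the plan says.** Objective 2.2.1 reads: "To assess the safety (at 6 months) of administering daunorubicin as continuous infusion under the proposed treatment regimen". Section 5.2.1 makes cardiac toxicity the matching outcome: an LVEF reduction of at least 10% from baseline together with an EF of 50% or less. It states that "these secondary outcomes will be assessed at the 6 month follow-up (or relapse) visit" and, on modality, "This assessment will be performed using both an ECHO and MRI measure".

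Section 6.6 sets the follow-up imaging. The 3-month scan is due at 3 months or relapse, whichever is first, with no further condition. The next sentence reads: "Patients still on protocol at 6 months post-treatment will have an MRI without contrast only". On-protocol status is not defined.

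Section 8.2 lists the imaging tasks without that condition: "MRI (at pre-induction visit, 3 month follow-up or relapse, at 6 month follow-up or relapse". The Appendix E worksheet likewise has a column for 6 months or relapse. Section 8.2 also makes every patient evaluable for toxicity from the first daunorubicin dose.

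For the analysis, section 13.2 says: "Similar toxicity analyses as described above for the primary objective will be examined at the 6-month time point". Section 13.1 describes those analyses as paired t-tests of change from baseline "to each of the available post-chemotherapy imaging assessment", plus an event proportion with a 95% confidence interval. For 6 months no denominator, missing-scan rule, handling of death or sensitivity analysis is given.

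**The concern.** Read literally, the plan measures 6-month cardiac safety only in patients who remain on protocol, and then analyses whoever was scanned. Some reasons for leaving could be related to the outcome. Section 6.6 provides for patients removed from the study for unacceptable adverse events and follows the event to resolution or stabilization, but requires no scan. Sections 6.1 and 8.2 remove patients with persistent leukemia after two inductions. These patients never reached remission, so the relapse scan does not cover them.

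What is at stake is interpretation. A 6-month rate below the 3-month rate could mean cardiac recovery, or only that affected patients were no longer scanned. As written, the analysis cannot separate the two. A patient who met the definition at 3 months and then left would be in neither the numerator nor the denominator at 6 months.

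**Working it through.** **1. The plan's own figures (section 13.3).** They reproduce, but they cover 3 months only.

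- Enrolment: 32 / (1 − 0.20) = 40.
- Paired t-test, noncentral t, two-sided 0.05, 80% power: detectable difference 0.511 SD at n = 32 and 0.454 SD at n = 40 (stated as 0.511 and 0.45).
- Clopper-Pearson half-width at 16/32: 0.181, as stated.

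No attrition or sample size is planned for 6 months.

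**2. Who has a stated 6-month scan.**

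| Group | What the documents say | 6-month scan |
|---|---|---|
| Still on protocol | 6.6 | Yes (MRI only in 6.6 and Appendix E; ECHO and MRI in 5.2.1) |
| Relapse | 5.2.1, 8.2 and Appendix E provide a scan at relapse; 6.6 adds the on-protocol condition | Conflict |
| Transplant | Ends treatment (6.5); effect on protocol status not stated | Unclear |
| Removed for unacceptable adverse event | Event followed (6.6) | None stated |
| Persistent leukemia after two inductions | Removed from study (6.1, 8.2) | None stated |

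**3. Why understatement is plausible.** Planned daunorubicin in the section 6.1 table is 3 × 60 = 180 mg/m² for induction and 2 × 60 = 120 mg/m² for re-induction. Patients removed after two inductions therefore have 180 + 120 = 300 mg/m² planned before any reduction. Those who stay are a mix of 180 and 300. Section 1.1 calls the cardiotoxicity cumulative. Removal for an adverse event may also be related to the outcome. This supports a direction but does not prove one.

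**4. Size under assumptions.** Let f be the share of treated patients without a 6-month scan, p_on the rate in scanned patients and p_off the rate in unscanned patients. None of these is in the documents. Then

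all-treated rate = (1 − f) × p_on + f × p_off.

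With p_on = 10%:

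| p_off / p_on | f = 20% (32 scanned) | f = 50% (20 scanned) |
|---|---|---|
| 0.5 | 9% | 7.5% |
| 1 | 10% | 10% |
| 2 | 12% | 15% |
| 3 | 14% | 20% |

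For example, 0.5 × 10% + 0.5 × 30% = 20%. Over this range the reported 10% is between 10 points too low and 2.5 points too high.

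**5. Bounds that assume nothing about the unscanned, over 40 treated patients.**

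- 3 events in 32 scanned: 3/40 = 7.5% to (3 + 8)/40 = 27.5%.
- 2 events in 20 scanned: 2/40 = 5% to (2 + 20)/40 = 55%.

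**6. Precision.** Going from n = 32 to n = 20, the worst-case half-width rises from 0.181 to 0.228 and the detectable difference from 0.511 to 0.660 SD.

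**7. What the remedies can and cannot do.** A simulation with assumed inputs: baseline EF normal with mean 60 and SD 6, truncated at 45; EF change mean −4, SD 6; 3-to-6-month correlation 0.7; event an absolute fall of 10 points with EF 50 or less; 30% of patients without a 3-month event leave.

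- True 6-month rate 10.8%. The on-protocol rate is about 8% if 70% of patients with a 3-month event leave, about 6.7% if 90% leave, and 10.8% (no bias) if 30% leave.
- A cumulative event counted from the scans obtained is about 14.5%, against a true cumulative 16.1%. It estimates a different quantity from the 6-month point rate and is still incomplete.
- For mean change, suppose 70% of those with a fall over 9 points and 25% of the rest leave. If leaving depends on the 3-month value, the completer mean is about −3.2 and a regression on that value returns −4.0. If it depends on the 6-month value, the same regression returns only about −3.3 to −3.4.

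**The case against.** The strongest reply is that section 6.5 lists ends of treatment, not of study participation. Section 6.6 speaks of patients on protocol at 6 months after treatment, so on protocol cannot simply mean on treatment. This stands. A reader might infer that transplanted patients are lost to the 6-month scan; the documents leave that open.

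A reader might also infer that relapsing patients drop out. The documents do not support this, because sections 5.2.1 and 8.2 and Appendix E plan a scan at relapse. What remains is the conflict with section 6.6 and the loss of any cardiac change after relapse.

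No section removes a patient for an EF fall, consolidation contains no daunorubicin, and with equal loss there is no bias. This also stands: the selection mechanism is possible, not documented.

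Events at 3 months are reported as the primary outcome, so they do not vanish from the trial. That is correct, but they are not carried into the 6-month result.

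Finally, this is a secondary, descriptive endpoint with no decision rule, and sampling error is large: the exact 95% interval for 2/20 is 1.2% to 31.7%. That limits the weight of the point but does not remove it. A confidence interval computed on the scanned patients does not reflect selection.

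**Conclusion.** The concern holds in a limited form. Section 6.6 ties the 6-month MRI to an undefined status and conflicts with three other places in the protocol. Section 13.2 then analyses available scans without a denominator or a missing-scan rule, although section 8.2 makes all treated patients evaluable for toxicity. At least two groups have no stated 6-month scan.

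It is tempting to conclude that late cardiotoxicity is understated. That needs a higher rate in unscanned patients, which the documents neither give nor exclude. Understatement is plausible because of the removals for adverse events and the higher planned exposure of patients removed after two inductions. The range from 10 points too low to 2.5 points too high rests wholly on the assumptions of a 10% scanned rate, 20% to 50% unscanned and a rate ratio of 0.5 to 3. The 3-month scan does not carry the on-protocol condition. The change is worth making, but the trial's main result does not depend on it.

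**What to change.** - Define on-protocol status, and reconcile section 6.6 with sections 5.2.1 and 8.2 and Appendix E, including the difference between ECHO plus MRI in 5.2.1 and MRI only in 6.6 and Appendix E.
- In section 13.2, keep the 6-month point proportion. Beside it, report the cumulative proportion meeting the definition on MRI at the 3-month, relapse or 6-month scan. Label it a separate estimand, use all treated patients as the denominator, and give best- and worst-case bounds for those not scanned.
- Tabulate patients without a 6-month scan by reason: adverse event, persistent leukemia, transplant, relapse, death, withdrawal, other.
- Estimate the 6-month mean change with a repeated-measures model on baseline, 3-month and 6-month MRI values, rather than by the completer paired t-test alone. State that it removes bias only under missing at random.

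The cost is revised wording, a little more programming, bounds that may be wide, and one untestable assumption to declare. No extra scan is needed.
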